1.7 Determination of sample size

The planned minimum sample size is 402 patients. The primary endpoint for the study is technical performance, assessed as a binary outcome procedural success Yes/No. Procedural success will be assessed at the anastomosis level; each patient may have > 1 anastomosis. Based on data published in the medical literature (see RASM Literature Review Report [5]), the traditional failure and complication rate for vascular anastomoses is 15%, implying a success rate of 85%. The study will have 85% power to conclude that a success rate using Symani of 89% (or higher) is better than the literature value if a minimum of 402 anastomoses operations are performed. The percentage success will be estimated and exact 95% confidence limits calculated. If the lower 95% confidence limit exceeds 85% then the conclusion can be reached that Symani is superior to manual surgical methods. As each patient may have more than one anastomosis operation, the number of anastomoses will be ≥ 402 from 402 patients, providing increased power. As the number of anastomoses/patient is unknown at the time of study design, the conservative approach of recruiting 402 patients has been followed.

The number of patients missing a response for the primary endpoint will be monitored and additional patients may be recruited if deemed necessary.

There will be no predetermined limit to the number of sites that can participate in the study. Patients enrolled under the retrospective data collection protocol addendum will contribute to the planned sample size for the entire study (prospective plus retrospective).

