2.4.4 Analysis of effectiveness variables

Note on analysis models/approach.

For all binary outcomes a simple frequency table presenting number and percentage (with confidence limits) will be produced, where the denominator will be the unit of analysis (patient, surgery type, procedure or anastomosis). The confidence limits produced will be biased as they assume independent observations whilst repeat assessments on the same patient (ie > 1 anastomosis/procedure, >1 procedure/patient) are not independent.

To explore the extent of dependence in the data, a table will be produced to describe the hierarchy in the data (as per fig 1), namely:

- Number of patients.
- Number of surgery types (flap, replantation, lymphatic)/patient (i.e. 1, 2 or 3 different types of surgery).
- Within surgery type, number of procedures/patient (i.e. number of flaps, number of replantations, number of lymphatic procedures).
- Within each procedure, number of anastomoses/procedure and also number of anastomoses/patient.

In the simplest scenario there will be one surgery type/patient, one procedure/patient and for that procedure only one anastomosis (so at all levels there is one/patient).

The most complex structure is each patient has all three surgery types, with multiple procedures of each type and for each procedure there are multiple anastomoses.

In addition to these levels of dependence due to repeated observations on the same patient, the results are expected to be influenced by surgeon. Accordingly, for the main analysis of all effectiveness endpoints, a mixed model will be employed where surgeon will be included as a random term.

All models will be fitted separately for each surgery type (free flaps, replantations, lymphatic).

In all models fixed effects for subpopulation (prospective/retrospective) and recipient site/location will also be included to facilitate estimation by subpopulation and recipient site/location. For analysis of replantations a further fixed effect will be included for procedure type (free or nerve).

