2.4.4.1 Analysis of primary effectiveness variable – procedure robotic success

As per section 2.1.3.1 each anastomosis for each patient in the FAS will be assigned to ‘Yes’ or ‘No’ for procedure robotic success. This represents a binary outcome. The analysis of this variable is at the anastomosis level.

For each surgery type (replantation, free flap or lymphatic surgery) stratified frequency tables will be presented stratified by subpopulation (prospective/retrospective) and recipient site/location. The denominator is the number of anastomoses. The proportion of anastomoses classified as a robotic success by stratum and overall for each surgery type will be presented with 95% confidence limits. Results will also be presented on a forest plot.

For replantations a further stratifying variable will be included, namely procedure type (free/nerve).

For each surgery type, a generalized linear mixed model (GLMM) will be used to estimate the percentage of anastomoses classified as robotic success. In SAS, PROC GLIMMIX will be utilized to analyze the data. Subpopulation (prospective/retrospective), recipient site/location and surgeon experience will be included as fixed effects, and surgeon as a random effect. Procedure number (within a surgery type) and anastomosis number (within a procedure) will be included as random terms to acknowledge the dependence in the data (see note above). From the model the adjusted rate of robotic success will be obtained, with 95% confidence limits, for each type of surgery overall and by recipient site/location, by surgeon experience and by subpopulation. (Model 1).

Fixed effects

For free flaps, recipient site will be head and neck, extremities, breast or other.

For lymphatic surgery location will be heads and neck, upper limbs or lower limbs

For replantations there will also be a factor for procedure type (free or nerve), as well as recipient site (as for free flaps) (Model 1a) and results also obtained by procedure type (free/nerve).

For all types of surgery, surgeon experience is classified as microsurgeon, fellow, resident.

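### The superiority rule in SAP 1.7 uses an exact interval that treats anastomoses as independent, and no overall cluster-adjusted estimate is planned or tied to the 85% threshold

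*SAP*

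**What the plan says.** **The rule.** SAP 1.7 assesses success at the anastomosis level. On the analysis it says "The percentage success will be estimated and exact 95% confidence limits calculated", and it permits a conclusion of superiority over manual methods if the lower limit is above 85%. On power it says "The study will have 85% power to conclude that a success rate using Symani of 89% (or higher) is better than the literature value", on condition "if a minimum of 402 anastomoses operations are performed". It then argues that "the number of anastomoses will be ≥ 402 from 402 patients, providing increased power", and calls recruiting 402 patients the conservative choice because the number of anastomoses per patient is unknown. SAP 1.5 records that the unit of the primary analysis was changed from patient to anastomosis.

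**The warning.** SAP 2.4.4 says of simple percentages with limits: "The confidence limits produced will be biased as they assume independent observations". It adds that surgeon is expected to influence results, and makes a mixed model with a random surgeon term the main analysis.

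**The models.** SAP 2.4.4 continues: "All models will be fitted separately for each surgery type (free flaps, replantations, lymphatic". SAP 2.4.4.1 (Model 1) obtains adjusted success rates with 95% limits overall within each surgery type and by subgroup. It also says that procedure number and "anastomosis number (within a procedure) will be included as random terms". Appendix 1 gives this model as Bernoulli with patient as the subject. SAP 2.5.1, by contrast, lists surgery type as a fixed factor where applicable.

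**The concern.** The only rule that leads to a superiority conclusion is attached to an interval of the kind that the SAP itself describes as biased. The analysis meant to deal with the dependence yields three separate rates, one per surgery type, and none of them is the single percentage that 1.7 compares with 85%. Section 2.5.1 points towards a pooled model, but none is written down. An analyst who follows 1.7 literally will report an interval that is too narrow whenever anastomoses within a patient, or patients of one surgeon, resemble each other. An analyst who follows 2.4.4.1 has no overall limit to apply. The choice between them would then be made with the data in hand.

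**Working it through.** **Inputs from SAP 1.7.** Null rate 0.85; alternative 0.89; n = 402; exact 95% limits, taken as two-sided, so 2.5% one-sided.

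**The rule with independent observations.** The smallest count whose exact lower limit exceeds 0.85 is 356 of 402 (88.6%; lower limit 0.8503; with 355 it is 0.8476). Then:
- P(X ≥ 356 | 0.85) = 2.40%, the nominal false-claim rate.
- P(X ≥ 356 | 0.89) = 64.9%, so the stated 85% power does not reproduce. It would at an alternative of 0.90 (85.2%). That is a separate matter and plays no part below.

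**Inputs that the documents do not give (assumptions).** Number of surgeons, 6 to 30; surgeon SD 0 to 0.7 and patient SD 1.0 on the logit scale; m = 1 to 3 anastomoses per patient.

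**Approximation.** With k patients per surgeon, surgeon correlation ρS and within-patient correlation ρP:

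DE = 1 + (m − 1)ρP + (k − 1)·m·ρS; effective size = 402m / DE; false-claim rate ≈ 1 − Φ(1.96/√DE).

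Take 10 surgeons (k = 40.2), ρS = 0.026 and ρP = 0.14, which correspond to about SD 0.5 (surgeon) and 1.0 (patient):

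| m | DE | Effective size | Approximate false-claim rate |
|---|---|---|---|
| 1 | 1 + 39.2 × 0.026 = 2.02 | 402/2.02 = 199 | 8.4% |
| 2 | 1 + 0.14 + 39.2 × 2 × 0.026 = 3.18 | 804/3.18 = 253 | 13.6% |
| 3 | 1 + 0.28 + 39.2 × 3 × 0.026 = 4.34 | 1206/4.34 = 278 | 17.3% |

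**Simulation.** Logit-normal surgeon and patient effects, marginal rate held at 0.85, 402 patients, exact rule from 1.7 (patient SD 1.0 throughout):

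| Scenario | m = 1 | m = 2 | m = 3 |
|---|---|---|---|
| No surgeon effect | 2.4% (exact) | about 2.7% | – |
| 20 surgeons, surgeon SD 0.3 | 3.2% | 4.6% | – |
| 10 surgeons, surgeon SD 0.5 | about 8% | 12–13% | 15–17% |
| 6 surgeons, surgeon SD 0.7 | – | – | 28–29% |

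The ranges in the third row are the spread between repeated runs. The simulated effective sizes in that row are about 206, 259 and 289, close to the approximation.

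A beta-binomial model gives the same picture. Patient clustering alone, with ICC 0.05 to 0.3, gives 2.6% to 5.7% for m = 2 to 3. With m = 2 and patient ICC 0.2, adding surgeon clustering gives about 5% (30 surgeons, surgeon ICC 0.01) to 15% (15 surgeons, surgeon ICC 0.05).

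**Whether Model 1 can supply the limit as it stands.**
- It is run by surgery type, so it gives no overall figure.
- With one binary row per anastomosis, a random term for anastomosis number is an observation-level effect whose variance the data cannot identify.
- The scale of the adjusted rate is not stated. If the random effects have a total SD of 1 on the logit scale, a rate of 88.6% at the average surgeon and patient corresponds to a population rate of 85%.

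**The case against.** **The SAP does address dependence.** A mixed model with random surgeon is its main analysis, and adjusted limits are planned for each surgery type. This stands. The gap is narrower: there is no pooled estimate, and no link from the adjusted analysis to the rule in 1.7.

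**The size is unknown.** A reader might infer that the false-claim rate is well above 2.5%. The documents do not support that as a finding. They give no correlation, surgeon count or number of anastomoses per patient, and SAP 1.7 sets no limit on sites. With 20 to 30 surgeons and small correlations the inflation is slight.

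**More anastomoses do add information.** A reader might infer that the power sentence in 1.7 is wrong in direction. It is not: in the 10-surgeon case the effective size rises from about 206 to 259 to 289 as m goes from 1 to 3. The fault is in counting the extra anastomoses as independent. The word conservative is also fair as regards the unknown number per patient, but it leaves out surgeon clustering.

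**Model 1 is partly protected.** SAP 2.4.4 brings in the procedure and anastomosis terms only as required, so the anastomosis term could be dropped under the existing text. With patient as the subject in Appendix 1, the procedure term acts as a patient intercept when each patient has one procedure. The remaining need is to state this in advance.

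**Three tests.** A reader might see three unadjusted tests against 85%. The SAP never says that the per-type limits are to be read that way.

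**The benchmark.** SAP 1.7 takes 85% from vascular anastomoses, while the study also covers nerve and lymphatic work. A better interval does not settle whether one threshold suits all three types.

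**Conclusion.** The point holds as an unresolved conflict within the SAP. The superiority rule uses limits that assume independence, SAP 2.4.4 calls limits of that kind biased, and no cluster-adjusted overall estimate is specified or named as the one compared with 85%. Where clustering exists, the interval from 1.7 is too narrow.

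The false-claim rate moves from about 2.4% to roughly 3% to 30% over the assumed range. The low end is patient clustering alone or many surgeons with little variation; the high end needs 6 surgeons, large surgeon variation and three anastomoses per patient. The mechanism is certain and the size is not. Surgeon clustering contributes most, and it can bring the effective size below 402 even with one anastomosis per patient. This should be settled before analysis, because the superiority conclusion depends on it.

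**What to change.** - **SAP 2.4.4.1:** prespecify one confirmatory quantity, the overall population-averaged proportion of robotic success, with a 95% interval that allows for patient and surgeon clustering. One suitable choice is a cluster-robust interval by surgeon with a small-sample t correction. Choose a single method.
- **SAP 1.7, rule:** refer to the lower limit of that interval. Label the naive exact limits and the per-type limits descriptive.
- **SAP 1.7, sample size:** keep the statement that additional anastomoses add information. Add that they are correlated, and that surgeon clustering can bring the effective size below 402, so 402 patients is not conservative in that respect.
- **SAP 2.4.4 and 2.5.1:** reconcile separate models by surgery type with surgery type as a fixed factor.
- **Model 1 and Appendix 1:** omit the anastomosis-number random term from the Bernoulli model, keep a patient-level intercept, and state whether adjusted rates are conditional or population-averaged.

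The cost is SAP wording, one more model and a wider interval. No further data collection is needed. The change does not resolve whether the vascular benchmark suits nerve and lymphatic anastomoses.

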2. STATISTICAL AND ANALYTICAL PROCEDURE

The study has a hierarchical structure as follows:

- There are three types of surgery: free flaps, replantations, and lymphatic. A patient may have more than one type of surgery (e.g flap and replantation).
- Within a type of surgery, e.g. free flaps, a patient may have more than one procedure during an operation.
- Within each procedure, anastomoses are performed. More than one anastomosis may be performed within a procedure.

For the purpose of this SAP, endpoints may be defined at any of these levels, i.e. patient, surgery type, procedure within a surgery type, anastomosis within procedure. This hierarchy is described in Figure 1. The unit of analysis for each endpoint will be clearly defined in this SAP.

Sponsor: MMI Product: Symani system for microsurgical anastomosis Study: PRIMO	
Statistical Analysis Plan Final 22 November 2024	

Figure 1 hierarchy of dependence in the endpoint data.

Level			
Surgery type within patient	Free flap	Replantation	Lymphatic
Procedure within surgery type	FF1, FF2, FF3 etc	R1, R2, R3 etc	LVA1, LVA2, LVA3 etc
Anastomosis within procedure	FF1A1, FF1A2, FF2A1, FF2A2, FF3A1, FF3A2, etc	R1A1, R1A2, R2A1, R2A2, R3A1, R3A2, etc	LVA1A1, LVA1A2, LVA2A1, LVA2A2, LVA3A1, LVA3A2, etc

In addition to this hierarchical structure regarding the initial attempt, for a particular anastomosis, there may be the need for an intraoperative redo within the same operation (a secondary endpoint), or the need for a re-operation on a subsequent date (a secondary endpoint). This patient flow is described in Figure 2.

[figure not shown]

Sponsor: MMI Product: Symani system for microsurgical anastomosis Study: PRIMO	
Statistical Analysis Plan Final 22 November 2024	

Figure 2. Patient flow through study procedures

Note. Procedure = flap or replantation or lymphatic. [1] There may be > 1 procedure done. A second procedure may be the same type as procedure 1 (e.g 2 flaps procedures) or may be different. The figure suggests 2 procedures (due to space limitations) but there may be > 2 procedures.

Sponsor: MMI Product: Symani system for microsurgical anastomosis Study: PRIMO	
Statistical Analysis Plan Final 22 November 2024	

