2.1.3.2.3 Intraoperative need to redo the anastomosis (yes or no)

Castor' and Dendrite's anastomosis form has a question 'timing of anastomosis', with the options 'first attempt' and 'subsequent attempt'. Subsequent attempt is a redo form.

Redo forms will be 'aligned' with first attempt forms by matching anastomosis type (free flap, replantation) according to the form completed and with surgery type by matching the responses to the questions:

Side, vessel type and vessel diameter.

Sponsor: MMI Product: Symani system for microsurgical anastomosis Study: PRIMO	
Statistical Analysis Plan Final 22 November 2024	

For lymphatic surgery matching will be done using type (lymphatic anastomosis form completed), type of anastomosis and vein diameter.

Any anastomosis which has at least one redo form will be classified as redo="yes".

Any anastomosis which does not have a matching form for subsequent attempt will be classified as redo="No".

If there are subsequent attempt forms which do not directly align with a first attempt form, this will be resolved by clinical review so all subsequent attempt forms are aligned with a first attempt form.

For this analysis, the anastomosis is the unit of analysis.

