2.1.3.5.2 Intra-operative anastomosis patency

For each anastomosis, Dendrite form R or Castor Anastomosis Data Form asks the question 'Success of anastomosis'. If the response is 'Patent' then intraoperative patency = Yes.

If response = 'failed' or 're-done' then intraoperative patency = No.

Note, this endpoint will only be assessed using the index operation where the timing of anastomosis = 'First attempt'.

The unit of analysis is the anastomosis.

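### The SAP's rule for intra-operative redo has no same-operation condition, so an anastomosis revised at a later operation can be counted as an intra-operative redo

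*SAP*

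**What the plan says.** The protocol synopsis lists the intra-operative need to redo an anastomosis as a secondary endpoint for replantations, free flaps and lymphatic surgery. It is listed separately from the post-operative need to redo.

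SAP section 2 keeps that separation. It distinguishes two events that can follow a first attempt: "need for an intraoperative redo within the same operation (a secondary endpoint), or the need for a re-operation on a subsequent date".

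SAP 2.1.3.2.3 then derives the intra-operative endpoint from the timing question on the anastomosis form:

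- The source is any form with the second answer option: "Subsequent attempt is a redo form".
- For free flaps and replantations, redo forms are matched to first attempts by form type and by "Side, vessel type and vessel diameter". In lymphatic cases the keys are the form type, the kind of anastomosis and the diameter of the vein.
- One matched form is enough: "Any anastomosis which has at least one redo form will be classified as redo" = yes.
- Forms that find no match go to clinical review, "so all subsequent attempt forms are aligned with a first attempt form".

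SAP 2.4.4.2.3 and Appendix 1 send the result to Model 1/1a at anastomosis level and add no further selection.

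**The concern.** The definition depends on which operation the redo took place in, and the derivation never looks at the operation. A revision at a return to theatre two days after surgery, if entered on a subsequent-attempt form, would match its first attempt on side, vessel type and diameter and be classed as an intra-operative redo. If a re-operation form is also completed, the same event counts in the 7-day endpoint of SAP 2.1.3.2.4. A revision on day 10 would count as an intra-operative redo although it falls outside the 7-day endpoint.

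At stake is the meaning of a protocol-named secondary endpoint. A rate that mixes revisions on the table with later ones is too high for what it claims to measure, and the error runs against the device.

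**Working it through.** The plan states no figure for this endpoint, so there is nothing to reproduce. The check is mainly a comparison of sections.

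**1. Is there a same-operation condition in the rule?** No. The keys in SAP 2.1.3.2.3 are form type, side, vessel type and diameter, or for lymphatic surgery form type, anastomosis type and vein diameter. Operation, date and OR visit are absent.

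**2. Can a form from a later operation drop out at review?** Not as written. The stated result of review is that all subsequent-attempt forms are attached to a first attempt. No outcome is provided for a form that belongs to another operation.

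**3. Does the SAP foresee anastomosis work at later operations?** Yes.

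- SAP 2.1.3 allows several operations within the initial stay.
- SAP 2.1.3.1 has an anastomosis form completed for each anastomosis, and 2.1.3.2.2 places these data within a procedure within an operation.
- SAP 2.5.5 provides for revision of a robotic anastomosis before discharge.
- For patency, SAP 2.1.3.5.2 says that "this endpoint will only be assessed using the index operation", and only first attempts.

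**4. Do the documents say that sites mark a revision at a return to theatre as a subsequent attempt?** No. SAP 2.1.3.2.4 describes separate, dated re-operation forms. Whether an anastomosis form is also completed, and how its timing question is answered, is not stated.

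Steps 1 to 3 show that the rule can misclassify. Step 4 means that the documents do not show how often it would.

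**5. Illustration of size, free flaps only.**

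Added rate per anastomosis = re-operation rate × share of re-operations that redo one anastomosis and record it as a subsequent attempt ÷ anastomoses per flap.

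- Re-operation rate: 10.7% (95% limits 9.8% to 11.7%), the registry figure in SAP 2.4.6.2.4. Applying it per flap is an assumption.
- Share and anastomoses per flap: assumptions. The documents give neither.

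Percentage points added at 10.7%:

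| Share | 1 per flap | 2 per flap | 3 per flap |
|---|---|---|---|
| 25% | 2.7 | 1.3 | 0.9 |
| 50% | 5.4 | 2.7 | 1.8 |
| 100% | 10.7 | 5.4 | 3.6 |

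With a share of 25% to 50% and 2 to 3 anastomoses per flap, the range runs from 0.107 × 0.25 / 3 = 0.0089 to 0.107 × 0.50 / 2 = 0.0268, or 0.9 to 2.7 points. At the registry's confidence limits it is 0.098 × 0.25 / 3 = 0.8 to 0.117 × 0.50 / 2 = 2.9 points. If no anastomosis is redone both on the table and later, an assumed true rate of 2% would appear as 2 + 0.9 = 2.9% to 2 + 2.7 = 4.7%. With such overlap the rise would be smaller, because each anastomosis counts once.

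**The case against.** The strongest defence is that the intent is plain. The section is headed as intra-operative redo, section 2 defines the event as within one operation, and SAP 2.1.3 says that the Figure 2 flow will be used to assess the timing of procedures. Figure 2 is not shown in the text available, so it may draw the line clearly. This carries some weight, but the general sentence does not become a key or an exclusion in 2.1.3.2.3. The instruction to align every form leaves no place for one, and a programmer will follow the derivation.

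The second defence is that the necessary event is undocumented: no section says that sites complete a subsequent-attempt form at a return to theatre. This stands. A reader might infer that later redos are in fact being reported as intra-operative. The documents support only that they can be.

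The patency restriction is also weaker evidence than it looks. Its first-attempt condition already excludes redo forms, so the index-operation condition shows only that first-attempt forms from later operations are foreseen.

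A reader might also infer that the trial could no longer separate failure on the table from later failure. That does not follow. Patency in 2.1.3.5.2 uses first attempts at the index operation and classes failed or redone anastomoses as not patent. The 7-day redo (2.1.3.2.4) and the 30-day re-operation rate (2.1.5.1.4) have their own sources. None of the three uses the redo-matching rule.

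Finally, the size rests mostly on assumed inputs. The registry figure is an overall re-operation rate whose definition is not given. The SAP's own 30-day re-operation endpoint includes donor-site operations, which need not involve an anastomosis. Nothing comparable is available for replantation or lymphatic surgery.

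**Conclusion.** The point holds in a limited form. The rule in SAP 2.1.3.2.3 does not implement the distinction drawn in SAP section 2. It has no operation or date condition, and its last step attaches every subsequent-attempt form to a first attempt. Where a later revision is entered on such a form, it counts as an intra-operative redo and may count again in the 7-day endpoint.

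The possible bias is upward and confined to the intra-operative redo rate. Its size cannot be determined from the documents; it could be nil if sites never use subsequent-attempt forms at re-operations. The 0.9 to 2.7 points for free flaps is an illustration under the stated assumptions, and the finding does not depend on it. The change is worth making because the written rule conflicts with the written definition.

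**What to change.** In SAP 2.1.3.2.3:

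1. Add the operation (same date and same OR visit) to the matching keys for all three surgery types. The date alone would not separate a same-day return to theatre, so the recorded start and end times are needed too.
2. Count a subsequent-attempt form as an intra-operative redo only when it belongs to the same operation as the matched first attempt.
3. Limit the clinical-review alignment to forms from the same operation.
4. Exclude forms from later operations from this endpoint. Use them only as supporting evidence in the clinical review that 2.1.3.2.4 already provides for when a re-operation form is missing. They should not become a second routine source for that procedure-level endpoint.

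The cost is a few sentences in the SAP and one more key in the programs. SAP 2.1.3 already has the date, start time and end time of each operation recorded, so no new data are required. The sponsor should confirm from the case report forms that each anastomosis form can be linked to its operation in both data-capture systems. If Figure 2 already carries the intended rule, the same text makes it explicit.
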